****I. Study Background:****

Restless Legs Syndrome (RLS) is a common complication in uremic patients, significantly impacting their quality of life and prognosis. Many studies have found that RLS is closely related to nocturnal hypertension and the occurrence of cardiovascular events in uremic patients, affects patient sleep, leads to anxiety, depression, and decreased quality of life. The mortality rate of hemodialysis (HD) patients with RLS is significantly higher than that of patients without RLS [1]. Over the past few decades, dopaminergic drugs have been the mainstay of first-line treatment for RLS. Although these drugs show significant short-term efficacy, long-term use is characterized by short half-life, susceptibility to early morning rebound, and poor long-term efficacy [2, 3]. Recent studies suggest that nucleoside equilibrative transporter inhibitors, such as dipyridamole and ticagrelor, may control RLS symptoms by increasing endogenous adenosine-mediated tonic A1 receptor activation, potentially representing a new treatment strategy for RLS [4, 5]. Preliminary clinical studies have demonstrated that dipyridamole significantly improves patients' sleep quality and quality of life [6].

We will only screen patients who meet both the inclusion and exclusion criteria to participate in this study. Enrolled patients will receive dipyridamole free of charge, 50 mg each time, three times a day, for a total of 12 weeks. During the treatment period, we will regularly follow up on

the participants' condition. Participants will need to undergo assessments using the International Restless Legs Syndrome Study Group Rating Scale (IRLS), Clinical Global Impression scale (CGI), Medical Outcomes Study Sleep Scale (MOS-SS), etc., before and after treatment to evaluate the degree of symptom change. Through this treatment, we aim to understand the specific efficacy of dipyridamole in uremic patients with RLS, the extent to which the drug improves RLS sensory and motor symptoms and sleep conditions, observe the impact of dipyridamole on concomitant depression, anxiety, quality of life, etc., in maintenance dialysis patients, and also understand the efficacy and common adverse reactions of dipyridamole in clinical use in maintenance dialysis patients.

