****II. Study Objectives****

To understand the efficacy and adverse reactions of dipyridamole in uremic patients with RLS, and its effects on concomitant depression, anxiety, sleep disorders, and quality of life in these patients.

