****III. Study Design and Methods:****

****1. Study Population:**** This is a single-center, self-controlled study. We plan to recruit 80 patients with uremia and RLS who are undergoing maintenance hemodialysis at the Blood Purification Center of the First Affiliated Hospital of Chongqing Medical University from July 2025 to December 2025.

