****Inclusion Criteria:****

- (1). Maintenance hemodialysis ≥ 3 months;
- (2). Age between 18-75 years;
- (3). Diagnosed with RLS according to the IRLSSG criteria and with an IRLS score > 15 points;
- (4). Willing to cooperate with this study.

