****2. Study Procedure:****

- (1) Screen patients undergoing maintenance hemodialysis at our hospital's dialysis center whose baseline International Restless Legs Syndrome Study Group Rating Scale (IRLS) score is >15 points.
- (2) Patients who meet the inclusion criteria and are willing to sign the informed consent form.
- (3) Collect general clinical data and pre-treatment laboratory parameters, including age, gender, body mass index, Charlson Comorbidity Index score, dialysis duration, serum iron, ferritin, serum parathyroid hormone, hemoglobin, albumin, and dialysis adequacy. Assess changes in patient condition before and after treatment using scales such as the International Restless Legs Syndrome Study Group Rating Scale (IRLS), Pittsburgh Sleep Quality Index (PSQI), Hamilton Depression Rating Scale (HAMD), Hamilton Anxiety Rating Scale (HAMA), Clinical Global Impression scale (CGI), Medical Outcomes Study Sleep Scale (MOS-SS), Epworth Sleepiness Scale (ESS), and KDQOL-SF™-36.
- (4) All enrolled RLS patients will be instructed by designated personnel to orally take dipyridamole tablets, 50mg each time, three times a day, for a continuous period of 12 weeks.
- (5) Collect information on the occurrence of drug-related adverse reactions during the study period, such as nausea, headache, dizziness, diarrhea, insomnia, fatigue, bleeding, etc. The follow-up period is 12 weeks.
- (6) After the treatment concludes, collect the patients' general clinical data and laboratory parameters again.
- (7) Statistical Analysis: Measurement data conforming to a normal distribution will be expressed as mean \pm standard deviation ($\bar{x} \pm s$). Count data will be expressed as frequencies. Comparisons of means before and after treatment will be performed using paired-sample t-tests. Comparisons of rates before and after treatment will be performed using paired-sample chi-square tests. A P-value < 0.05 will be considered statistically significant. All statistical analyses will be performed using SPSS software.
- (8) Evaluate changes in patient condition before and after treatment. Primary evaluation indicators: complete remission rate, partial remission rate, overall response rate, incidence of adverse events, dropout rate.

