****3. Sample Size Calculation:****

$$\text{Formula: } n = [(Z \alpha / 2 + Z \beta) * \sigma / \Delta]^2$$

Where n is the sample size, $Z \alpha / 2$ is the two-sided quantile of the normal distribution corresponding to the significance level α (usually $\alpha = 0.05$, so $Z \alpha / 2 = 1.96$). $Z \beta$ is the quantile

of the normal distribution corresponding to the power ($1 - \beta$) (power is usually set at 0.8, so $Z\beta = 0.84$). σ is the standard deviation of the observation indicator, reflecting data dispersion. Δ is the expected mean difference before and after treatment, i.e., the minimum difference expected to be detected. Based on literature review and preliminary studies, we set $\sigma = 4$ and $\Delta = 2$. Therefore, the calculated sample size $n = 31.36$. Rounding up, $n=32$. Considering potential dropouts, the sample size needs to be increased by 10%-20%, so the final sample size is set at 80.

4. Data Analysis and Statistical Methods:

Conduct statistical analysis on the obtained data: Measurement data conforming to a normal distribution will be expressed as mean \pm standard deviation ($\bar{x} \pm s$). Count data will be expressed as frequencies. Comparisons of means before and after treatment will be performed using paired-sample t-tests. Comparisons of rates before and after treatment will be performed using chi-square tests. A P-value < 0.05 will be considered statistically significant.

Study Flowchart:

Patient Screening

↓

Collection of Patient Clinical and Laboratory Data

↓

Oral Administration of Dipyridamole Tablets under Guidance

↓ (12 weeks)

Collection of Drug-Related Adverse Reactions during the Study

↓

Post-Treatment Collection of General Clinical Data and Laboratory Parameters

↓

Statistical Analysis, Efficacy Evaluation, Manuscript Preparation

5. Safety Analysis and Content Evaluation:

Follow up and statistics on the types, number of cases, and severity grading of potential adverse reactions during dipyridamole treatment. Evaluate the causes of these adverse reactions and their causal relationship with the study drug. Calculate the incidence of adverse reactions. Main adverse reactions may include headache, dizziness, gastrointestinal discomfort (nausea, vomiting, diarrhea), hypotension, bleeding tendency, allergic reactions, etc.

6. Observation Indicators:

Primary Indicators: Restless Legs Syndrome symptom severity score (IRLS).

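### The protocol aims at the drug's efficacy, but a one-group before-after comparison in patients selected on a high IRLS score can show only that scores changed

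*Protocol*

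**What the plan says.** **The aim.** Section I of the protocol states "we aim to understand the specific efficacy of dipyridamole in uremic patients with RLS" and also "the extent to which the drug improves RLS sensory and motor symptoms and sleep conditions". Section II opens "To understand the efficacy and adverse reactions of dipyridamole in uremic patients with RLS" and goes on to the drug's effects on depression, anxiety, sleep disorders and quality of life.

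**The design.** Section III.1 says "This is a single-center, self-controlled study". Under Section III.2, item (4), "All enrolled RLS patients will be instructed by designated personnel to orally take dipyridamole tablets". The planned course and the follow-up are both 12 weeks.

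**Entry and outcome.** Inclusion criterion (3) is "Diagnosed with RLS according to the IRLSSG criteria and with an IRLS score > 15 points". Section III.6 names the IRLS score as the primary indicator. Its secondary indicators are also scales, and Section VII confirms that efficacy is judged mainly through scales.

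**The test.** Sections III.2, item (7), and III.4 both say "Comparisons of means before and after treatment will be performed using paired-sample t-tests", with significance at P < 0.05. In Section III.3 the planning difference of 2 points is a mean difference between before and after treatment.

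**Not described anywhere.** The protocol mentions no concurrent control, placebo, untreated run-in, repeated baseline, blinded rater or outside benchmark for improvement without the drug. It does not say that its conclusions will be limited to before-after change.

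**The concern.** The quantity that is estimated is not the quantity that is claimed. The mean before-after change is a sum: any effect of the drug, plus expectation, plus extra attention from the study team, plus natural fluctuation, plus regression to the mean. A paired t-test asks whether that sum is zero. The aim asks about the first term alone.

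Regression to the mean is built in. Patients are admitted because their IRLS score is high on one occasion, and the same scale is then the primary outcome. Some average fall is expected on re-rating even if nothing has been done.

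If a significant P-value were reported as evidence that dipyridamole works in dialysis patients with RLS, the error rate of that statement would not be 5%. It would depend on the size of the non-drug terms, which the study does not measure. A later analysis plan cannot repair this, because aim, comparator and rating times belong to the protocol and no data are collected for the missing comparison.

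**Working it through.** **1. The plan's own figure.** Section III.3 gives Z values 1.96 and 0.84, sigma = 4 and delta = 2. n = [(1.96 + 0.84) × 4 / 2]² = 5.6² = 31.36, rounded up to 32. This reproduces. It is the correct formula for detecting a before-after change. The final size of 80 is taken as stated.

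**2. Smallest significant mean fall.** The formula is t(0.975, n−1) × SD / √n. The protocol calls sigma the standard deviation of the observation indicator. Using it as the SD of the change is an assumption, so 8 is shown beside it.

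| n | SD of change | Smallest significant mean fall |
|---|---|---|
| 80 | 4 | 1.990 × 4/√80 = 0.89 |
| 64 (20% lost) | 4 | 1.998 × 4/√64 = 1.00 |
| 80 | 8 | 1.990 × 8/√80 = 1.78 |

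**3. Chance of a significant improvement when the drug adds nothing.** Let d be the mean non-drug improvement. The documents give no value, so a range is assumed; 2 points equals the planning delta. The probability is the upper tail of a noncentral t with n−1 degrees of freedom and noncentrality d√n / SD, beyond t(0.975, n−1).

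| d (points) | n = 80, SD 4 | n = 64, SD 4 | n = 80, SD 8 |
|---|---|---|---|
| 0.5 | 20% | 17% | 8% |
| 1 | 60% | 50% | 20% |
| 1.5 | 91% | 84% | 38% |
| 2 | 99% | 98% | 60% |
| 3 | >99% | >99% | 91% |

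At d = 0 the figure is 2.5%, as it should be for one direction of a two-sided 5% test.

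**4. How large regression to the mean could be.** Assume that scores in the screened pool are normal with mean μ and SD s, and that two ratings correlate at r. With a = (15 − μ)/s and λ = φ(a)/[1 − Φ(a)], the expected fall from selecting scores above 15 is (1 − r) × s × λ. The documents supply none of μ, s or r; the ranges are assumed as μ 12 to 20, s 6 to 8, r 0.7 to 0.9.

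- Smallest (μ = 20, s = 6, r = 0.9): 0.1 × 6 × 0.353 = 0.21 points.
- Middle (μ = 15, s = 6, r = 0.8): 0.2 × 6 × 0.798 = 0.96 points.
- Largest (μ = 12, s = 8, r = 0.7): 0.3 × 8 × 1.051 = 2.52 points.

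With the SD of change held at 4 and n = 80, the chance of significance from this source alone runs from 7% through 56% to above 99%. An SD of 4 does not fit every combination. The model itself implies a variance of change of (1 − r)² × s²(1 + aλ − λ²) + s²(1 − r²). Using that instead, the chance runs from about 10% to about 98% across the same grid. The width of the range shows that the protocol gives no means of judging the size of this component.

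**The case against.** **The design is declared.** The protocol calls itself self-controlled and defines its planning difference as before versus after. Section III.2, item (8), speaks of evaluating changes in condition. That stands, and a one-group before-after study is acceptable for a descriptive aim. It does not help here, because the written aims are not descriptive.

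**The word specific may be a translation of concrete.** This is a fair point. A reader might infer that the protocol promises an effect net of placebo, but the documents do not support resting the case on that one adjective. The mismatch remains without it, since the text also speaks of efficacy, of how far the drug improves symptoms, and of its effects.

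**The protocol never says that P < 0.05 proves efficacy.** Correct: it says only that such a result is statistically significant. A reader might infer that an inert tablet would be declared effective, but that predicts a future report. What the documents do show is that nothing in them guards against that conclusion.

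**The percentages are an ordinary power curve.** They are, and they rest on an assumed non-drug change and on reading sigma as the SD of change. They show what the test responds to. They are not an estimated false-positive rate for this trial.

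**The drug has already been tested against placebo.** The reference list includes a randomized, placebo-controlled crossover study in RLS. That is relevant background, but it supplies no control data for these dialysis patients.

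**A rating after the drug is stopped could settle the matter.** A reader might infer this, but it would not. Patients would know that they had stopped, so worsening is open to the same expectation, and sustained improvement could be carry-over. Section VII also promises long-term follow-up and treatment guidance without saying who will be off the drug. Nor does item (6) of Section III.2, "After the treatment concludes, collect the patients' general clinical data and laboratory parameters again", bear on this, since it concerns clinical and laboratory data and not the scales.

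**Conclusion.** The point holds as a mismatch between aim and design. Sections I and II claim a causal effect; Section III delivers an uncontrolled, in effect open-label, change from baseline on subjective scales, in patients selected on the outcome scale. Open-label is not the protocol's word, but it follows from giving every patient the named drug with no masking described.

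That drug effect and non-drug change cannot be separated depends on no assumed number. Its practical size does: at n = 80, a non-drug improvement equal to the planning delta of 2 points would be significant with probability about 99% if the SD of change is 4, and about 60% if it is 8. Enlarging the sample raises these figures and offers no protection. The documents do not support saying how large the non-drug change will be, or that the drug has no effect. The data remain valid as a description of within-patient change.

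**What to change.** 1. In Sections I and II, restate the aim as describing the within-patient change in IRLS and the other scores during 12 weeks of open-label dipyridamole.
2. In Section III.4, add that the mean change will be reported with its 95% confidence interval.
3. State in the protocol that P < 0.05 shows a change from baseline; that with no control group, and with entry restricted to IRLS above 15, this change cannot be attributed to the drug; and that it will not be reported as proof of efficacy.

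The cost is wording and a less favourable claim. Recruitment, sample size, test and visits are unchanged.

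Keeping the causal aim would need a concurrent control and a new sample size. With the protocol's own sigma of 4 (as the SD of change), delta of 2, alpha and power, that is 2 × 31.36 = 62.72, so 63 per arm and 126 in total before dropout, against the 80 planned. Rewording is therefore the proportionate change for the study as designed.

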****II. Study Objectives****

To understand the efficacy and adverse reactions of dipyridamole in uremic patients with RLS, and its effects on concomitant depression, anxiety, sleep disorders, and quality of life in these patients.

****III. Study Design and Methods:****

****1. Study Population:**** This is a single-center, self-controlled study. We plan to recruit 80 patients with uremia and RLS who are undergoing maintenance hemodialysis at the Blood Purification Center of the First Affiliated Hospital of Chongqing Medical University from July 2025 to December 2025.

****Inclusion Criteria:****

- (1). Maintenance hemodialysis ≥ 3 months;
- (2). Age between 18-75 years;
- (3). Diagnosed with RLS according to the IRLSSG criteria and with an IRLS score > 15 points;
- (4). Willing to cooperate with this study.

****Exclusion Criteria:****

- (1). Comorbid with other cerebrovascular, muscular, or motor system diseases that affect the

assessment of RLS severity;

- (2). Comorbid with active bleeding, such as gastrointestinal bleeding, cerebral hemorrhage, etc.;
- (3). Patients already on long-term dipyridamole treatment;
- (4). Use of other medications that may affect RLS severity within the past 3 weeks, such as dopamine receptor agonists/antagonists, tricyclic antidepressants, lithium, etc.;
- (5). Patients with a history of psychiatric disorders;
- (6). Pregnant or lactating women;
- (7). Patients allergic to or intolerant of dipyridamole;
- (8). Patients unable or unwilling to cooperate with this study.

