Secondary Indicators: Quality of life score (KDQOL-SF-36), Clinical Global Impression scale (CGI) score, Medical Outcomes Study Sleep Scale (MOS-SS) score, Pittsburgh Sleep Quality Index (PSQI) score, Epworth Sleepiness Scale (ESS) score, Hamilton Anxiety Rating Scale (HAMA) score, Hamilton Depression Rating Scale (HAMD) score, Self-Rating Anxiety Scale (SAS) score, Self-Rating Depression Scale (SDS) score.

Safety Indicators:

- ① Occurrence of adverse reactions: including but not limited to headache, dizziness, gastrointestinal discomfort (nausea, vomiting, abdominal pain, diarrhea), hypotension, bleeding

tendency (gingival bleeding, epistaxis, subcutaneous bruising, etc.), allergic reactions (rash, pruritus, dyspnea, etc.).

② Laboratory parameter monitoring:

* Hematological indicators: Regularly test complete blood count (including red blood cell count, hemoglobin, platelet count, etc.) and coagulation function (prothrombin time, activated partial thromboplastin time, fibrinogen, etc.) to monitor whether dipyridamole's antiplatelet aggregation effect increases bleeding risk or causes hematological abnormalities.

* Biochemical indicators: Test liver and kidney function parameters (e.g., ALT, AST, serum creatinine, blood urea nitrogen, etc.) to assess the drug's impact on liver and kidney function; monitor electrolytes (e.g., potassium, sodium, chloride, etc.) to observe if drug effects or changes in uremia condition lead to electrolyte disturbances.

③ Vital signs monitoring:

* Monitoring content: Regularly measure patients' blood pressure, heart rate, respiratory rate, body temperature, and other vital signs, with particular attention to blood pressure changes, alert for hypotension caused by the vasodilatory effect of dipyridamole.

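### Exclusion (2) bars only active bleeding, so a patient whose gastrointestinal or other non-cerebral bleed has recently stopped passes every written criterion (minor, cheap safety improvement)

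*Protocol*

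**What the plan says.** The only eligibility criterion about bleeding is exclusion (2) in Section III.1: "Comorbid with active bleeding, such as gastrointestinal bleeding, cerebral hemorrhage, etc". It gives no time window.

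Two other exclusions might seem to help. Exclusion (1) covers patients "Comorbid with other cerebrovascular, muscular, or motor system diseases that affect the" assessment of RLS severity. Exclusion (8) covers "Patients unable or unwilling to cooperate with this study".

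Enrolled patients are to "orally take dipyridamole tablets, 50mg each time, three times a day, for a continuous period of 12 weeks" (Section III.2(4)).

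The protocol treats bleeding as a possible harm of the drug in four places:
- Section III.2(5) lists drug-related reactions to be collected: "such as nausea, headache, dizziness, diarrhea, insomnia, fatigue, bleeding, etc".
- Section III.5 lists among the main expected reactions "gastrointestinal discomfort (nausea, vomiting, diarrhea), hypotension, bleeding tendency, allergic reactions, etc".
- Section III.6 gives the reason for blood count and coagulation tests: to see whether the drug's "antiplatelet aggregation effect increases bleeding risk or causes hematological abnormalities".
- Section IV puts gastrointestinal bleeding and cerebral hemorrhage first among the bleeding events a patient may have.

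**The concern.** The two bleeds that exclusion (2) gives as examples are the same two that Section IV lists first as risks of treatment. The criterion therefore aims at the right harm, but on its plain wording it stops applying once the bleeding stops.

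A patient whose gastrointestinal bleed ended shortly before screening could be started on a drug with an antiplatelet effect. The monitoring in Section III.6 and the physician intervention in Section IV act during treatment, so they could find a re-bleed only after exposure.

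Consistency is also at stake. Section VI(1) gives research assistants the preliminary screening against the written criteria, and two screeners may read an undefined word differently.

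A lesser point concerns interpretation. Adverse-event incidence is a primary evaluation indicator in Section III.2(8), Section III.5 requires a causal judgement, and there is no concurrent control. A re-bleed in a patient who had just bled would be hard to attribute. No size is claimed for this.

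**Working it through.** The protocol states no figure on this point, so the check is to apply the written criteria to two test patients who are otherwise eligible.

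**Patient A: a gastrointestinal bleed that stopped shortly before screening.**
1. Inclusion (1) to (4) cover dialysis duration, age, RLS diagnosis with IRLS score, and willingness. None concerns bleeding (0 of 4).
2. Exclusion (1) covers cerebrovascular, muscular or motor disease that affects RLS assessment. It does not apply.
3. Exclusion (2) covers active bleeding. The bleed has stopped, so on the plain wording it does not apply.
4. Exclusions (3) to (7) cover long-term dipyridamole, other drugs that affect RLS, psychiatric history, pregnancy or lactation, and allergy or intolerance to dipyridamole. None applies.
5. Exclusion (8) concerns cooperation only. It gives the investigator no general discretion on safety grounds.

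Result: not excluded.

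**Patient B: a cerebral hemorrhage that has stopped.** Exclusion (1) applies only if the event affects the assessment of RLS severity; otherwise the result is as for patient A. The gap is therefore clearest for non-cerebral bleeds.

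**Count.** Of 8 exclusions, 1 names bleeding and 0 set a bleed-free interval. The same list does look back elsewhere: exclusion (4) uses 3 weeks for drugs that affect RLS severity, and exclusion (5) refers to a history of psychiatric disorder. Beside these, the word active most naturally means current.

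**Safeguards before treatment.** Section III.2(3) collects hemoglobin, serum iron, ferritin and a comorbidity score. No threshold on any of them is a condition of entry.

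**Planned exposure of a patient so admitted** (regimen from Section III.2(4)):
- 3 × 50 mg = 150 mg per day
- 12 × 7 = 84 days
- 3 × 84 = 252 doses

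This is the regimen of every participant. It shows what the patient would receive and does not measure any excess risk.

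**The case against.** The strongest reply is that exclusion (2) states nothing false and contradicts nothing else in the protocol. Active is an ordinary clinical word, and a bleed only just stopped or still under treatment may fairly be judged active. Candidates are known to the centre, which already follows them with routine laboratory tests (Section VII), and baseline hemoglobin and iron data are taken. A physician may withhold the drug on judgement. Much of this stands, and it is why the point is minor. It does not close the gap, because none of these protections is a written entry rule.

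Three stronger readings are tempting, and the protocol does not support them:

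- A reader might infer that a recent bleed is shown to carry a materially higher risk on this dose. The protocol gives no bleeding rate, no dose relation and no prior-bleed risk factor. Section III.6 treats the effect on bleeding risk as something to be monitored.
- A reader might infer that a particular interval, such as 3 months, is required. The protocol gives no length.
- A reader might infer that a stricter criterion costs nothing because the sample has room to spare. With the inputs of Section III.3, n = [(1.96 + 0.84) × 4 / 2]² = 31.36, rounded up to 32, and allowing for 20% dropout gives 32 / (1 − 0.20) = 40. The protocol says "the sample size needs to be increased by 10%-20%, so the final sample size is set at 80". But 40 serves only the comparison of a mean before and after treatment. Section III.2(8) also names remission and response rates, adverse-event incidence and dropout as primary evaluation indicators, and no sample size is derived for them. The protocol also does not say how many eligible patients the centre has.

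**Conclusion.** The point holds as a minor, low-cost improvement to patient safety. Followed as written, exclusion (2) admits an otherwise eligible patient whose gastrointestinal or other non-cerebral bleed has recently stopped, although the protocol itself names bleeding as a possible harm of the drug. Some patients with a past cerebral hemorrhage are caught by exclusion (1).

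The conclusion rests on one assumption: that active means bleeding at the time of screening. If the investigators already read it to include a recent bleed, the change only puts that practice in writing.

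Neither the number of patients affected nor the added risk can be computed from the protocol. The planned analysis is not affected.

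**What to change.** Reword exclusion (2) along these lines: *Active bleeding, or clinically significant bleeding (such as gastrointestinal or intracranial) within a fixed interval before the first dose.* The investigators should set the interval on clinical grounds; 3 months is only an example. Check it at screening by patient history and available records. History is needed because records may not cover the whole interval for a patient who came from another centre.

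The cost is one reworded criterion and one history question, with no new test. The downside is possibly slightly fewer eligible patients at this single centre during the July to December 2025 recruitment period, in a number the protocol does not allow to be computed.

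### Other RLS-affecting drugs are controlled only before entry; their use during the 12 weeks is not named for collection or accounted for, so their effect falls into the before-after result.

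*Protocol*

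**What the plan says.** Under Exclusion Criteria, item (4) excludes patients with "Use of other medications that may affect RLS severity within the past 3 weeks", and gives dopamine agonists and antagonists, tricyclic antidepressants and lithium as examples. This is the only place where the protocol controls other drugs that act on RLS.

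Section III describes the design: "This is a single-center, self-controlled study". Under Study Procedure, dipyridamole is given "three times a day, for a continuous period of 12 weeks".

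The same section lists what is collected:
- Item (3), baseline: "Collect general clinical data and pre-treatment laboratory parameters, including age, gender, body mass index, Charlson Comorbidity Index score, dialysis duration, serum iron, ferritin", followed by further laboratory values and the rating scales. No medication is named.
- Item (5), during treatment: drug-related adverse reactions. "The follow-up period is 12 weeks".
- Item (6), at the end: "After the treatment concludes, collect the patients' general clinical data and laboratory parameters again".

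Item (8) sets the evaluation: "Evaluate changes in patient condition before and after treatment", with complete remission, partial remission and overall response among the primary evaluation indicators. Section III.6 names IRLS as the primary indicator, and means are compared by paired t-test.

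**The concern.** The protocol judges these drugs able to distort RLS severity, since it excludes patients for recent use. It then says nothing about them over the 12 weeks in which the outcome accrues. In a randomised trial, similar use in a control arm would at least partly cancel. Here there is no such arm, so a drug started after baseline acts only on the after value, and the whole of its effect enters the paired difference.

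Such use is plausible on the protocol's own description. The Study Background calls dopaminergic drugs the mainstay of first-line treatment and credits them with clear short-term efficacy. Patients enter with IRLS above 15, without these drugs in the preceding 3 weeks, and under regular care at the same unit. A patient whose symptoms persist could be given one, improve on it, and be scored as a remission or response on dipyridamole. Tricyclic antidepressants are also on the exclusion list, so the depression and anxiety scales are exposed in the same way.

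**Working it through.** **1. The plan's own figure.** Section III.3 uses 1.96 and 0.84 for the normal quantiles, σ = 4 and Δ = 2:

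n = [(1.96 + 0.84) × 4 / 2]² = 5.6² = 31.36, rounded up to 32.

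This reproduces. The stated recruitment target is 80.

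**2. What is controlled, and when.**

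| Period | Control or collection of other RLS-affecting drugs |
|---|---|
| 3 weeks before entry | Exclusion criterion (4) |
| Baseline, item (3) | Not named |
| Weeks 0 to 12, item (5) | Not named; adverse reactions only |
| End of treatment, item (6) | Not named; general clinical data and laboratory values |
| Analysis, item (7) and section III.4 | Not accounted for |

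**3. Size of the bias, for illustration.** The documents give neither the share of patients who start such a drug (f) nor its effect on IRLS (e), so both are assumed. The shift in the mean change is f × e, positive if the drug relieves RLS and negative if it worsens it.

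- f = 10%, e = 10 points: 0.10 × 10 = 1.0 point
- f = 5%, e = 5 points: 0.05 × 5 = 0.25 points
- f = 20%, e = 10 points: 0.20 × 10 = 2.0 points

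If Δ = 2 is in IRLS points, these are 50%, 12.5% and 100% of it. Drugs that worsen RLS give the same sizes with the opposite sign, and a mixture partly cancels: 10% × 10 − 5% × 5 = 1.0 − 0.25 = 0.75 points.

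**4. Effect on the test, same assumptions.** Suppose dipyridamole has no effect, the standard deviation of the change is otherwise 4, and all added drugs relieve RLS. The mean change is f × e and its standard deviation is √(16 + f(1 − f)e²). For f = 10% and e = 10 this is √(16 + 9) = 5, so the noncentrality at n = 80 is 1.0/5 × √80 = 1.79. The chance of P < 0.05 in the two-sided paired t-test (noncentral t) is:

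| f, e | Shift | n = 32 | n = 80 |
|---|---|---|---|
| 5%, 5 | 0.25 | 6% | 8% |
| 10%, 10 | 1.0 | 20% | 42% |
| 20%, 10 | 2.0 | 49% | 88% |

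The nominal level is 5%. The larger sample makes this worse, because a fixed bias is detected more surely as n grows.

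**The case against.** **The data may be recoverable.** Section VIII names patient medical records as a data source, section VII says that all patients are treated and followed at this one centre, and the item (3) list is introduced as an inclusive one, so general clinical data could include medication. This stands in part. A reader might infer that the use goes unrecorded and can never be reconstructed; the documents do not support that. They show only that it is not named for collection. Drugs obtained elsewhere, and exact dates, may still be missed.

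**The direction is not fixed.** A reader might also infer that the bias always flatters dipyridamole. Criterion (4) does not support that: it lists dopamine agonists and antagonists together, adds tricyclic antidepressants and lithium, and gives no direction of effect. This objection stands. The upward direction rests on the added drug being one that relieves RLS.

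**The mechanism is assumed.** The protocol describes no rescue provision. Patients who do badly may withdraw instead, which section VI (5) allows at any stage. This stands as a limit on any statement of size.

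**Handling belongs in an analysis plan.** How such patients are analysed could be set out there, and one may exist. But an analysis plan can only use data that are collected, and asking for starts and dates is a matter of study conduct for the protocol.

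**It is one instance of a wider limit.** Without a control group, no outside cause of change can be separated from the drug. That is true, but this cause is one the protocol itself identifies and can cheaply record.

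**Conclusion.** The gap is real. The protocol controls other RLS-affecting drugs up to entry and then neither names them for collection nor accounts for them. In a single-arm before-after comparison, their effect falls wholly into the IRLS change and the remission and response rates attributed to dipyridamole.

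The bias runs in favour of dipyridamole for drugs that relieve RLS and against it for drugs that worsen RLS. Its size cannot be derived from the documents. The shifts of 0.25 to 2.0 points and the error rates above rest on assumed frequencies and effects, and on relieving drugs only. The comparison with Δ = 2 also assumes that Δ is in IRLS points, since section III.3 ties σ to an unnamed observation indicator. The point should be addressed before recruitment proceeds further, while prospective recording is still possible.

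**What to change.** Which drugs are permitted during the study, and all clinical care, stay with the sponsor. The changes concern recording and analysis only.

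- **Recording.** In Study Procedure items (3), (5) and (6), add a dated record of every start, stop or dose change of a drug covered by exclusion (4), from baseline to week 12, taken from the centre's records and from asking the patient.
- **Reporting.** State how many patients are affected.
- **Response rates.** Count patients who started or increased an RLS-relieving drug as non-responders in the remission and response rates.
- **IRLS.** Repeat the paired comparison with zero change for those patients. Carrying forward the last IRLS before the drug was started is not a separate option: the scales are specified only before and after treatment, so that value would be the baseline.
- **Drugs that may worsen RLS.** Report results with and without the patients concerned. Setting their change to zero could itself inflate the estimate.
- **Classification.** Decide which drugs count as relieving or worsening before the outcomes are examined.

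The cost is one case-report-form field, one extra analysis and possibly a slightly smaller effect estimate.
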